5.2 Handling of Missing Data

The mixed-effect model repeated measure (MMRM) assumes data are missing at random (MAR), which is a reasonable assumption in longitudinal clinical trials in MDD¹. However, the possibility of “missing not at random” (MNAR) data can never be ruled out. As sensitivity analyses, selection model², pattern-mixture model^{3,4,5,6}, and/or shared parameter model⁷ will be used to explore data missing mechanisms of MNAR and investigate the response profile of dropout patients by last dropout reason under MNAR mechanism for the following 3 scenarios: 1) Dropout reasons due to either AE or LOE as MNAR, 2) Dropout reasons due to either AE or LOE or subject withdrew consent as MNAR, 3) All dropouts as MNAR using

SAP 405-201-00014

both 1) Delta adjustment imputation method which is to departure from MAR assumption by progressively increasing the delta until conclusion from the primary analysis is overturned, and 2) Placebo based imputation methods in which missing data for both placebo and drug group are imputed based on the imputation model derived from placebo data. If drug improved outcomes prior to dropout, this benefit is carried into subsequent imputed values, but will diminish over time in accordance with the correlation structure. Details are provided in [Section 8.1.3 Sensitivity Analysis](#). The observed-cases (OC) data set will consist of actual observations recorded at each visit during the double-blind treatment period and no missing data will be imputed. MMRM, Wu-Bailey, and pattern-mixture model will be performed on the OC dataset.

The last-observation-carried-forward (LOCF) data set will include data recorded at a scheduled double-blind treatment period visit or, if no observation is recorded at that visit, data carried forward from the previous scheduled double-blind treatment period visit. Baseline data (e.g., the last visit of the single-blind placebo run-in period) will not be carried forward to impute missing values for the LOCF data set. The analysis of covariance (ANCOVA) analysis will be performed for the change from baseline to the end of the double-blind treatment period (Day 42, LOCF) in AISRS total score as sensitivity analysis. The ANCOVA_LOCF model includes treatment and study center as main effects, and baseline value as a covariate.

ANCOVA analysis with OC data will also be conducted on change from baseline for AISRS total score, as well as all continuous change from baseline efficacy endpoints.

For Clinical Global Impression (CGI) Change from Baseline and categorical response/remission variables, OC analyses will be performed in addition to LOCF analyses. Study center will not be included in the models for OC analyses.

6 Study Conduct

6.1 Subject Disposition, Completion Rate and Reasons for Discontinuation

Subject disposition will be summarized for the Randomized Sample by treatment group, and by center.

Subject completion rate and reasons for discontinuation will be summarized for the Randomized Sample by treatment group for the double-blind treatment period.

6.2 Treatment Compliance

For each subject, compliance in taking IMP is calculated by dividing the number of tablets taken by the total number of tablets the patients were scheduled to take during the double-blind

SAP 405-201-00014

treatment period. Compliance is calculated on double-blind IMP for the double-blind treatment period. For lost-to-follow up patients, the last IMP end date record will be used as the treatment end date.

Summary of Treatment compliance will be provided based on both eCRF data and AiCure captured data, respectively.

6.3 Protocol Deviation

Protocol deviations are summarized by center and type of deviation for randomized subjects by treatment group. Listing of protocol deviation will list the treatment phases during which the deviations occurred. In addition, protocol deviations affected by the COVID-19 will be summarized. Listing of subjects with protocol deviations affected by the COVID-19 will also be provided.

7 Baseline Characteristics

7.1 Baseline Definition

Baseline for the single-blind placebo run-in period refers to last available measurement prior to the start of administration of placebo in the single-blind placebo run-in period.

For analyses of the double-blind treatment period data, the baseline is defined as the last available measurement prior to the first dose of double-blind Investigational Medicinal Product (IMP) in the double-blind treatment period.

7.2 Demographic Characteristics

For the Randomized Sample, demographic characteristics will be summarized by treatment group. Age, race, ethnicity, height, weight, waist circumference, and body mass index (BMI) will be tabulated by gender and overall using the baseline assessments for the single-blind placebo run-in period.

Mean, range and standard deviation will be used to describe continuous variables such as age. Frequency distributions will be tabulated for categorical variables such as race.

7.3 Medical and Psychiatric History

A summary of medical and psychiatric history will be presented for the Randomized Sample by treatment group and overall.

A summary of the Adult ADHD Clinical Diagnostic Scale (ACDS) at screening will also be presented for the Randomized Sample (by treatment group and overall). The number and

SAP 405-201-00014

percentage of patients with each response to items A23-A41 from Section A (Childhood ADHD Symptoms Summary), B22-B39 from Section B (Adult ADHD Symptoms Summary), and C1-C5 will be presented.

7.4 Neuropsychiatric Diagnosis

A summary of MINI International Neuropsychiatric Interview (M.I.N.I.) will be presented for the Randomized Sample by treatment group and overall. Summarized will be the number and percentage of patients who meet each diagnosis criteria, and number and percentage of patients with each primary diagnosis.

7.5 Baseline Psychiatric Evaluation

For the Randomized Sample, baseline for the single-blind placebo run-in period and baseline for the double-blind treatment period psychiatric scale evaluation will be summarized by treatment group and overall. The mean, median, range and standard deviation will be used to summarize the assessments of: AISRS total score, ASRS and CGI - Severity of Illness Score (CGI-S).

8 Efficacy Analysis

All efficacy analyses pertaining to the double-blind treatment period will be performed on the Efficacy Sample, and patients will be included in the treatment group as randomized.

For analysis of the double-blind treatment period data, the baseline for the double-blind treatment period defined in [Section 7.1](#) will be used. Statistical comparisons are based on 2-sided, 0.05 significance levels.

8.1 Primary Efficacy Endpoint

The primary efficacy endpoint is the change from the baseline of the double-blind treatment period to Day 42 in AISRS total score.

8.1.1 Primary Efficacy Analysis

The objective of the primary efficacy analysis is to compare the efficacy between centanafadine (SR 200 mg TDD or SR 400 mg TDD) and placebo.

The primary estimand defining the treatment effect of interest in the trial uses the hypothetical strategy specified in the draft ICH E9 (R1) Addendum. The objective of the primary analysis is to evaluate the efficacy of centanafadine SR 400mg TDD in adult subjects with ADHD

SAP 405-201-00014

versus placebo. The estimand, or target of estimation, following the hypothetical strategy is the pharmacological effect seen, had no withdrawals occurred. This hypothetical estimand is justifiable in this case, since the focus is on the pharmacological effect of the drug additional to non-specific effects. Subjects who withdraw from a symptomatic IMP treatment either could have lost their treatment effect, had the subjects not taken any other symptomatic medication after withdrawal, or could have their treatment effect been masked, had the subjects taken other symptomatic medication after withdrawal. This means that any observations taken after subjects stop IMP will most likely not contribute relevant information about the pharmacological effect of the drug. Due to this strategy, the last collected efficacy assessment after premature trial discontinuation will be done only once at the ET Visit. Every effort will be made to complete all of the ET evaluations prior to administering any additional medications for the treatment of ADHD or other prohibited medications. In the case of terminal or lost to follow-up events, no ET evaluations would be expected, and only scheduled assessments performed before such an event has occurred.

The primary estimand for this trial is defined by the following components:

- Target Population: Efficacy Sample
- Endpoint: Change from baseline to Day 42 in the AISRS total score
- Intercurrent Events: Premature treatment discontinuation
- Measure of Intervention Effect: Difference in endpoint means between centanafadine (SR 200 mg TDD or SR 400 mg TDD) and placebo.

In this hypothetical strategy, the event of withdrawing IMP is considered missing at random (MAR), and the primary endpoint of the trial could be considered as a combination of the responses of on-treatment completers at Day 42 and the imputation of the endpoint to Day 42 following the trend in each treatment group using the MMRM method for subjects who withdraw IMP during the trial. All data collected during the trial treatment period will be used for statistical analysis. For the primary efficacy analysis, the treatment effect will be estimated using the MMRM method described below. Under the MAR assumption, MMRM provides an unbiased estimate of treatment effect for the treatment period. Analyses with missing values imputed by multiple imputation under MNAR and other methods will be performed as sensitivity analyses. The primary analysis will be performed on Efficacy Sample which includes all randomized subjects who took at least 1 dose of IMP in the double-blind treatment period and who have both a baseline for the double-blind treatment period and at least one post-randomization AISRS total score during the double-blind treatment period. The primary efficacy analysis will be performed by fitting a MMRM analysis with an unstructured (UN) variance covariance structure in which the change from baseline for the double-blind

SAP 405-201-00014

treatment period in AISRS total score at the scheduled double-blind treatment period visits will be the dependent variable based on the OC data set. The model will include fixed class effect terms for treatment, study center, visit day, and an interaction term of treatment by visit day. The model will also include the interaction term of baseline values for the double-blind treatment period of AISRS Total score by visit day as covariates. The primary comparison between centanafadine (400 mg TDD group or 200 mg TDD group) and placebo at Day 42 in the double-blind treatment period will be estimated as the difference between Least Squares (LS) means utilizing the computing software SAS procedure PROC MIXED.

In case there is a convergence problem with MMRM model with the unstructured (UN) variance covariance matrix, the following structures other than unstructured will be used in order of 1) heterogeneous toeplitz (TOEPH), 2) heterogeneous autoregressive of order 1 (ARH1), and 3) heterogeneous compound symmetry (CSH) and the first (co)variance structure converging to the best fit will be used as the primary analysis. If a structured covariance has to be used, the empirical “sandwich” estimator of the standard error of the fixed effects parameters will be used in order to deal with possible model misspecification of the covariance matrix.

Small centers will be defined as centers that do not have at least one evaluable subject (evaluable with regard to the primary efficacy variable) in each treatment arm in the double-blind treatment period. All small centers will be pooled to form “pseudo centers” for the purpose of analysis according to the following algorithm. Small centers will be ordered from the largest to the smallest based on the number of evaluable subjects (i.e., subjects who have baseline and at least one post-baseline value for the primary endpoint in the double-blind treatment period). The process will start by pooling the largest of the small centers with the smallest of the small centers until a non-small center is formed. This process will be repeated using the centers left out of the previous pass. In case of ties in center size, the center with the smallest center code will be selected. If any centers are left out at the end of this process, they will be pooled with the smallest pseudo centers, or if no pseudo centers exist, they will be pooled with the smallest non-small center.

8.1.2 Technical Computation Details for Primary Efficacy Analysis

The SAS code for the PROC MIXED procedure to carry out the above MMRM analysis with an unstructured variance covariance structure is illustrated as follows:

```
proc mixed;
  class treatment center visit subjid;
  model change=treatment center visit treatment*visit baseline*visit / s cl
  ddfm=kenwardroger;
  repeated visit /type=un subject=subjid r rcorr;
```

SAP 405-201-00014

```
lsmeans treatment*visit / pdiff cl alpha=0.05 slice=visit;
run;
```

where baseline is the last AISRS Total score prior to the first dose of double-blind IMP in the double-blind treatment period.

8.1.3 Sensitivity Analyses

8.1.3.1 Sensitivity Analyses for Missing at Random (MAR) Assumption

Traditionally the dropout mechanisms are divided into three types (Little, 1995): (1) Missing Completely at Random (MCAR), in which the probability of dropout doesn't depend on the observed data and the missing data; (2) Missing at Random (MAR), in which the probability of dropout depends on the observed data, and (3) Missing Not at Random (MNAR), where the probability of dropout depends on the missing data and possibly the observed data.

Most of MNAR methods (Diggle P, Kenward MG, 1994) have treated all observations with dropout as if they fall within the same dropout type. In practice, we would find that different dropout reasons may be related to the outcomes in different ways, for example, detailed dropout reasons for this study are: adverse events (AE), lack of efficacy (LOE), lost to follow-up, protocol deviation, sponsor discontinued study, subject met (protocol specified) withdrawal criteria, subject was withdrawn from participation by the investigator, and subject withdrew consent to participate. Dropout due to an AE and LOE may lead to MNAR dropout. Subject withdrew consent may also lead to MNAR dropout. However, it is debatable whether a dropout caused by subjects withdrew consent is MAR or MNAR. Except AE, LOE, and subject withdrew consent, all the other dropout reasons may be assumed as either MCAR or MAR dropout. Missing data due to COVID-19 will also be assumed as MAR.

As sensitivity analyses for missing at random (MAR) assumption, analyses for missing not at random (MNAR) will be carried out. Pattern Mixture Models (PMM) based on Multiple Imputation (MI) with mixed missing data mechanisms will be used to investigate the response profile of dropout patients by last dropout reason under MNAR mechanism for the following three scenarios:

- 1) Dropout reasons due to either AE or LOE as MNAR
- 2) Dropout reasons due to either AE or LOE or subject withdrew consent as MNAR
- 3) All dropouts as MNAR

Delta Adjustment Imputation Methods

This MNAR sensitivity analysis is to departure from MAR assumption by progressively increasing the delta until conclusion from the primary analysis is overturned. The delta is 0%, 10%, 20%, 30%, ..., 100% of the expected treatment difference of 5 points and/or the observed

SAP 405-201-00014

treatment difference between centanafadine and Placebo from the primary analysis of MMRM model until conclusion of the primary analysis is overturned. When $\delta=0$ it is MAR. When $\delta > 0$ it is MNAR.

- 1) Using Monte Carlo Markov Chain (MCMC) methodology from PROC MI to impute the intermittent missing data to a monotone missing pattern;
- 2) Using a standard MAR-based multiple imputation approach from PROC MI to impute the monotone missingness data
- 3) For patients in the treated group and with a dropout reason of AE or LOE or subject withdrew consent, a delta will be added for all the values after the dropout time.
- 4) Using MMRM model in the primary analysis to analyze the completed data using PROC MIXED on the multiple imputed data
- 5) Obtaining the overall results using PROC MIANALYZE.

Placebo Based Imputation Methods

Similar to “Standard” multiple imputations, except parameters for imputation model obtained from only the placebo (control) group. Missing data for both placebo and drug group are imputed based on the imputation model derived from placebo data. If drug improved outcomes prior to dropout, this benefit is carried into subsequent imputed values, but will diminish over time in accordance with the correlation structure.

In addition, model based MNAR methods such as the shared parameter model ([Wu and Baily, 1989](#)) and random coefficient pattern mixture model ([Hedeker D, Gibbons RD, 1997](#)) will be also performed.

LOCF and OC Analyses

Change from baseline of the double-blind treatment period for the AISRS total score will be evaluated using ANCOVA with baseline of the double-blind treatment period value as covariate and treatment and, in LOCF analyses, study center as main effects. For the OC analyses, study center will not be included in the model.

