The mixed-effect model repeated measures (MMRM) assumes data are missing at random (MAR), which is a reasonable assumption in longitudinal clinical trials in ADHD. However, the possibility of “missing not at random” (MNAR) data can never be ruled out. As sensitivity analyses, either selection model⁴¹ pattern-mixture model^{42,43,44,45} or shared parameter model⁴⁶ will be used to explore data missing mechanisms of MNAR and investigate the response profile of dropout reason. Pattern Mixture Models based on Multiple Imputation (MI) with mixed missing data mechanisms will be used to investigate the response profile of dropout subjects by last dropout reason under MNAR mechanism for the following 3 scenarios: 1) Dropout reasons due to either AE or lack of efficacy as MNAR, 2) Dropout reasons due to either AE or lack of efficacy or subject withdrew consent as MNAR, 3) All dropouts as MNAR using both 1) Delta adjustment imputation method which is to departure from MAR assumption by progressively increasing the delta until conclusion from the primary analysis is overturned, and 2) Placebo based imputation methods in which missing data for both placebo and drug group are imputed based on the imputation model derived from placebo data. If drug improved outcomes prior to dropout, this benefit is carried into subsequent imputed values, but will diminish over time in accordance with the correlation structure. Details of these exploratory analyses will be provided in the statistical analysis plan (SAP).

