- 2) Using a standard MAR-based multiple imputation approach from PROC MI to impute the monotone missingness data
- 3) For subjects in the treated group and with a dropout reason of AE or LOE or subject withdrew consent, a delta will be added for all the values after the dropout time.
- 4) Using MMRM model in the primary analysis to analyzed the completed data using PROC MIXED on the multiple imputed data
- 5) Obtaining the overall results using PROC MIANALYZE

Placebo Based Imputation Methods

The placebo-based imputation methods will be similar to the “Standard” multiple imputations method, except the parameters for the imputation model will only be obtained from the placebo (control) group. Missing data for both the placebo and drug groups are imputed based on the imputation model derived from placebo data. If drug improved the outcomes prior to dropout, this benefit is carried into subsequent imputed values, but will diminish over time in accordance with the correlation structure.

In addition, model based MNAR methods such as the shared parameter model⁴⁶ and random coefficient pattern mixture model⁴⁴ will be also performed.

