- CT-5.10.2 Summary of Mean Change from Baseline of the Double-Blind Treatment Period to the Double-Blind Treatment Period by Study Day in Adult ADHD Investigator Symptom Rating Scale (AISRS) Total Score - GEE (Efficacy Sample)
- CT-5.10.3 Summary of Mean Change from Baseline of the Double-Blind Treatment Period to the Double-Blind Treatment Period by Study Day in Adult ADHD Investigator Symptom Rating Scale (AISRS) Total Score - WGEE (Efficacy Sample)
- CT-5.11.1 Sensitivity Analysis of MNAR using Pattern Mixture Model with Multiple Imputation (Delta Method 1) in AISRS Total Score Assume All Dropouts as MNAR (Efficacy Sample)
- CT-5.11.2 Sensitivity Analysis of MNAR using Pattern Mixture Model with Multiple Imputation (Delta Method 2) in AISRS Total Score Assume All Dropouts as MNAR (Efficacy Sample)
- CT-5.11.3 Sensitivity Analysis of MNAR using Pattern Mixture Model with Multiple Imputation (Delta Method 1) in AISRS Total Score Dropout due to AE or LOE or Withdrew Consent as MNAR (Efficacy Sample)
- CT-5.11.4 Sensitivity Analysis of MNAR using Pattern Mixture Model with Multiple Imputation (Delta Method 2) in AISRS Total Score Dropout due to AE or LOE or Withdrew Consent as MNAR (Efficacy Sample)
- CT-5.11.5 Sensitivity Analysis of MNAR using Pattern Mixture Model with Multiple Imputation (Delta Method 1) in AISRS Total Score Dropouts due to AE or Lack of Efficacy (LOE) as MNAR (Efficacy Sample)
- CT-5.11.6 Sensitivity Analysis of MNAR using Pattern Mixture Model with Multiple Imputation (Delta Method 2) in AISRS Total Score Dropouts due to AE or Lack of Efficacy (LOE) as MNAR (Efficacy Sample)
- CT-5.11.7 Sensitivity Analysis of MNAR using Placebo Based Imputation in AISRS Total Score (Efficacy Sample)
- CT-5.11.8 Sensitivity Analysis of MNAR using Pattern Mixture Model with Multiple Imputation (Delta Method 1) in CGI-S Score Assume All Dropouts as MNAR (Efficacy Sample)
- CT-5.11.9 Sensitivity Analysis of MNAR using Pattern Mixture Model with Multiple Imputation (Delta Method 2) in CGI-S Score Assume All Dropouts as MNAR (Efficacy Sample)
- CT-5.11.10 Sensitivity Analysis of MNAR using Pattern Mixture Model with Multiple Imputation (Delta Method 1) in CGI-S Score Dropout due to AE or LOE or Withdrew Consent as MNAR (Efficacy Sample)
- CT-5.11.11 Sensitivity Analysis of MNAR using Pattern Mixture Model with Multiple Imputation (Delta Method 2) in CGI-S Score Dropout due to AE or LOE or Withdrew Consent as MNAR (Efficacy Sample)

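### Step 3 of the delta adjustment shifts only dropouts for AE, LOE or withdrawn consent, so it does not carry out the AE/LOE and all-dropouts scenarios; the listed deltas also end at 100% of the base although the aim is open-ended

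*SAP*

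**What the plan says.** SAP 8.1.3.1 lists three sets of dropout reasons to be treated as MNAR: (1) AE or LOE; (2) AE, LOE or withdrawn consent; (3) all dropouts. SAP 5.2 ties the same three to both delta adjustment and placebo-based imputation, and protocol 7.2 does likewise: "3) All dropouts as MNAR using both 1) Delta adjustment imputation method".

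One five-step delta algorithm follows. Only step 3 applies a shift: "For patients in the treated group and with a dropout reason of AE or LOE or subject withdrew consent, a delta will be added". Protocol 7.3.1.1.1 repeats it: "with a dropout reason of AE or LOE or subject withdrew consent, a delta will be added". Neither document gives a variant of step 3 for scenarios 1 and 3.

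SAP section 13 nevertheless plans delta tables for every scenario. Two AISRS tables end "in AISRS Total Score Assume All Dropouts as MNAR (Efficacy Sample" and two end "in AISRS Total Score Dropouts due to AE or Lack of Efficacy (LOE) as MNAR (Efficacy Sample".

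On the size of delta, SAP 5.2 speaks of "progressively increasing the delta until conclusion from the primary analysis is overturned". SAP 8.1.3.1 states the same aim and then lists the values: "The delta is 0%, 10%, 20%, 30%, ..., 100% of the expected treatment difference of 5 points and/or the observed". That sentence goes on to name the MMRM difference as the second base and closes with the same stopping condition.

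**The concern.** Step 3 is the operative rule, and it fixes one set of dropouts for all three scenarios. A program written from it would produce the same shifted data under three table titles.

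- **Scenario 3.** Dropouts for the other reasons listed in the SAP (loss to follow-up, protocol deviation, sponsor discontinuation, withdrawal criteria, investigator decision) would stay MAR in a table titled as treating all dropouts as MNAR. Fewer shifted subjects means a larger tipping delta, so the result looks more robust than that scenario is.
- **Scenario 1.** Consent withdrawals would be shifted although the title covers AE and LOE only, so the result looks less robust.

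The secondary matter is that the listed deltas have an end and the aim has none. If the list is taken as the limit, a result that survives 100% is reported without the departure from MAR that would overturn it, which is what the analysis is meant to find.

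**Working it through.** **1. Step 3 against the scenarios and tables**

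| Scenario (SAP 8.1.3.1) | AISRS tables | Second block | Step 3 fits? |
|---|---|---|---|
| 1: AE or LOE | CT-5.11.5, .6 | CT-5.11.12, .13 | No, too broad |
| 2: AE, LOE or consent | CT-5.11.3, .4 | CT-5.11.10, .11 | Yes |
| 3: all dropouts | CT-5.11.1, .2 | CT-5.11.8, .9 | No, too narrow |

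CT-5.11.7 and .14 are placebo-based and are not counted. For AISRS the mismatch is 4 of 6. Over both blocks it is 8 of 12, counting CT-5.11.12, whose title names an SDS mean score, apparently in place of CGI-S; without that table it is 7 of 11.

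The protocol has a further mismatch. Scenarios 1 and 2 in 7.3.1.1.1 also name rash. Protocol 7.2, the SAP scenarios and both versions of step 3 do not. Protocol step 3 therefore matches none of the three scenarios listed above it exactly.

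**2. The plan's own figure**

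Inputs (SAP section 4): difference 5, SD 12.5, 135 evaluable per arm, two-sided 0.05. SE = 12.5 × √(2/135) = 1.521; 5/1.521 = 3.286; power = Φ(3.286 − 1.960) = 0.908. The stated 90% is reproduced.

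**3. Formulas for the shift**

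Let f be the share of the treated arm that is shifted, D the primary difference and c the critical value. As an approximation to the multiple-imputation analysis, the shifted difference is D − f·δ and the tipping delta is (D − c·SE)/f.

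**4. Direction of the step 3 error (illustration only)**

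Take f = 1 − 292/405 = 0.279 for all dropouts (completers from protocol 3.3.1), D = 5 and SE = 1.521, so D − 1.96·SE = 2.018. The documents give no split of reasons, so the shares below are assumptions.

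| Set shifted | f | p at δ = 5 | Tipping delta, % of 5 |
|---|---|---|---|
| All dropouts (scenario 3 as titled) | 0.279 | 0.018 | 145% |
| Literal step 3, its reasons = 75% of dropouts | 0.209 | 0.009 | 193% |
| Literal step 3, its reasons = 50% of dropouts | 0.140 | 0.005 | 289% |
| AE/LOE only (scenario 1 as titled), = 25% of dropouts | 0.070 | 0.002 | 579% |

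If AE/LOE is 25% of dropouts and consent another 25%, literal step 3 in scenario 1 halves the tipping delta from 579% to 289%. In scenario 3 it raises it from 145% to 193-289%.

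**5. Does 100% suffice? Planning values**

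All dropouts shifted, D = 5. Two SEs bracket the case: complete data (135 per arm, 1.521) and completers only (292/3 = 97.3 per arm, 12.5 × √(2/97.3) = 1.792, so 5 − 1.96 × 1.792 = 1.488).

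| f | SE | Difference at δ = 5 | p | Tipping delta | % of 5 |
|---|---|---|---|---|---|
| 0.279 (292 of 405) | 1.521 | 3.60 | 0.018 | 2.018/0.279 = 7.23 | 145% |
| 0.279 | 1.792 | 3.60 | 0.044 | 1.488/0.279 = 5.33 | 107% |
| 0.351 (292 of 450) | 1.521 | 3.24 | 0.033 | 2.018/0.351 = 5.75 | 115% |
| 0.351 | 1.792 | 3.24 | 0.070 | 1.488/0.351 = 4.24 | 85% |

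**6. The same check on the appended results**

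Differences and SEs are from STAT-4.1.1, Day 42 counts from STAT-4.7. Everyone without a Day 42 value is shifted.

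- 400 mg: D = 4.4192, SE = 1.3220, df 378, f = 38/140 = 0.271. At δ = 5 the difference is 3.06, p = 0.021. Tip = (4.4192 − 1.966 × 1.3220)/0.271 = 6.70, or 134% of 5.
- 200 mg: D = 4.0055, SE = 1.2937, df 368, f = 27/140 = 0.193. At δ = 5 the difference is 3.04, p = 0.019. Tip = (4.0055 − 1.966 × 1.2937)/0.193 = 7.58, or 152% of 5.

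Adding the variance that the shift creates, δ²·f(1 − f)/140, lowers the tips to 6.54 (131%) and 7.34 (147%). As percentages of each dose's own observed difference they are 148-152% and 183-189%.

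**The case against.** **The intent is clear.** The scenario list stands directly above the algorithm, SAP 5.2 applies delta to all three scenarios, and each table title names its set. A careful programmer would vary step 3 by scenario. That stands as evidence of intent, but the rule as written does not carry it out. A reader might infer that the analyses were run on the wrong set. The documents do not show this, because none of the CT-5.11 output is included.

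**The count.** The algorithm sits under the primary endpoint and one base is 5 AISRS points, so 4 of 6 is the firm count. The 8 of 12 needs CT-5.11.12 read as CGI-S.

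**The grid.** A reader might infer a hard stop at 100% that can never yield a tipping delta for a result near the planned size. The text does not support that. The sentence listing the values ends with the until-overturned condition, so an open-ended reading exists. Nor do the planning values support it: with the larger SE and 35.1% shifted, the tip falls inside the list. What remains is that the two halves of the instruction pull apart and no rule covers a conclusion still standing at 100%.

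**A 100% bound is defensible.** At that point each shifted subject loses the whole assumed or observed effect, and surviving it is informative. This is fair, but it is a different aim from the one stated.

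**Conclusion.** Step 3 is a stated rule that gives wrong results for two of the three scenarios if followed. The direction is certain: too robust for all dropouts, not robust enough for AE/LOE. The size cannot be fixed from the documents, since the figures in step 4 of the working rest on assumed splits of dropout reasons.

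The end of the delta list is secondary. Whether 100% is enough depends on dropout and SE: about 85% to 145% of 5 points at planning values, and approximately 131-152% on the appended results, which is beyond the listed values for both doses. These figures approximate the imputation analysis and treat every missing Day 42 value as a dropout; narrower scenarios tip later. The planned 292 completers is a minimum, and protocol 3.10 counts a Day 42/ET visit as completion, so the planning shares are rough. With 20% shifted and SE 1.521 the tip would be 202%.

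Only this sensitivity analysis is touched. The primary test, alpha, and the placebo-based and model-based MNAR analyses are not. The change should be made.

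**What to change.** - Reword step 3 in SAP 8.1.3.1 and protocol 7.3.1.1.1 so that delta is added for *subjects in the treated group whose dropout reason is designated MNAR in the scenario being analysed*.
- Align the scenario lists across SAP 5.2 and 8.1.3.1 and protocol 7.2 and 7.3.1.1.1. Either name rash in all of them or state which listed reason a rash discontinuation falls under. Without this, the reworded step would apply different sets in the two documents.
- State that the 10% steps continue past 100% until p>=0.05 for each dose, and report the tipping delta.
- Correct the title of CT-5.11.12.
- If the tables have already been produced, state which dropout set each one used.

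The cost is a few edited sentences and a few more imputation runs.
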